8.2 Recording/Reporting requirements

8.2.1 Eliciting adverse event information

Research subjects will be routinely questioned about adverse events at all study visits and during follow-up telephone calls. Subjects will also be routinely asked to complete the headache pain scale.

8.2.2 Recording requirements

All observed or volunteered adverse events (serious or non-serious) and abnormal test findings, regardless of study group or suspected causal relationship to the study drug(s) will be recorded in the subjects’ case histories. For all adverse events, sufficient information will be pursued and/or obtained so as to permit 1) an adequate determination of the outcome of the event (i.e., whether the event should be classified as a *serious adverse event*) and; 2) an assessment of the causal relationship between the adverse event and the study drug(s).

Adverse events or abnormal test findings felt to be associated with the study drug(s) will be followed until the event (or its sequelae) or the abnormal test

finding resolves or stabilizes at a level acceptable to the safety assessing neurologist ([name] or [name]). Whichever neurologist is seeing the subject for assessments will not be the neurologist assessing safety for that subject. Each subject will have a separate examining neurologist and safety assessing neurologist. Monitoring and adjudication of all adverse events (serious or non-serious) will be performed in a sequential reporting manner. All patients will be provided a 24-hour hotline for reporting of any adverse effects. Initial screening will be performed by the clinical nursing team and all adverse events will be reported to the corresponding safety assessing neurologist for further evaluation. The treating and examining neurologists will not be involved in the notification of any adverse effects. Adjudication of all adverse events (serious or non-serious) will be determined by one of the safety assessments neurologist (sub-investigators [name] or [name]). Additionally, all serious adverse events will be reported to the DSMB immediately (24 to 48 hours) and they will adjudicate the adverse event and recommend unblinding, if necessary. Any non-serious adverse events will be reported to the DSMB on a half-yearly basis.

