5.1 Study drug compliance/adherence

All lumbar punctures will be performed by the treating clinician (the study PI, [name]) on an outpatient basis at Tisch MSRCNY. These appointments will be confirmed months in advance to ensure compliance. Whether the subject is receiving intrathecal injections of autologous MSC-NPs or getting placebo (only undergoing a lumbar puncture), each procedure will take approximately 20 minutes. Prior to all lumbar punctures, a trained infusion nurse will infuse patients with 1 gram of vancomycin and 80 mg of tobramycin to prevent the occurrence of meningitis. This infusion takes approximately four hours. Vancomycin is the drug of choice for *S. epidermidis*, a potential contaminant from the skin during the lumbar puncture procedure. It is also the drug used to treat penicillin-resistant *S. pneumoniae*. Vancomycin is also indicated in empiric use in meningitis until an organism has been identified. Tobramycin is synergistic with vancomycin and is also the treatment of choice for *pseudomonas* infections. Vancomycin and tobramycin are indicated for empiric treatment of neurosurgery-related meningitis at most institutions. Vital signs will be performed on both groups to monitor safety. These visits will last approximately 5 hours. Study subjects will be instructed to stay in bed and limit any physical activity for the 24 hours following each procedure. Patients will be asked to take Tylenol every 6 hours for two days after each treatment. Based on the data from our Phase I trial it is anticipated that patients may show signs of headache when given stem cells. Hence providing patients with Tylenol will help maximize patient blinding.

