Patients who have an intrathecal Medtronic pump installed for spasticity and pain management will be given the stem cells through the side port of the pump. The patient will be lying flat for the procedure with their pump exposed. The abdominal region where the pump is located is cleaned with betadine and a sterile drape is applied. A sterilized Medtronic Catheter Access Port Kit (Medtronic Inc product number 8540) will be used. The side port will be accessed with a 25-gauge non-coring needle. [name] will aspirate 1.5 mL of fluid from the side port to clear the catheter of any therapeutic drug in pathway that will be disposed of. CSF will be transferred to a 15ml specimen tube and transported to the laboratory for processing. The cells will be removed from the 1.5 ml transport vial using a 22-gauge needle 10cc syringe, re-suspended in 3 mL of preservative-free sterile saline and gently mixed by passage through a 22 gauge needle several times to break up any remaining cell clusters to ensure a uniform suspension. After the cells are injected through the side port, extra saline will be flushed through to make sure that the stem cells have been cleared out of the side port catheter. Following the procedure, a prime bolus will be administered via Medtronic programmer to ensure continuous supply of the patient's medicine. For the entirety of the procedure, the subject will be blindfolded, thus ensuring they remain blinded to the treatment.

Placebo group: For the six placebo treatment visits, subjects will undergo standard lumbar punctures as described above but with no cell injections. Ten mL of CSF will be collected for biomarker analysis at each lumbar puncture. The treating physician ([name]) will perform a mock procedure to imitate cell resuspension and delivery. Three ml of preservative-free sterile saline will be injected, and this will be given with up to 7 mL flush of preservative-free sterile saline. The entire procedure will take approximately 20 minutes. All subjects in the placebo group will get treated with antibiotics as well in the same regimen indicated above for the treatment group. The entirety of the procedure will take place posterior to study subject, thus ensuring they remain blinded to the treatment.

Patients who have an intrathecal Medtronic pump installed for spasticity and pain management will be given the placebo through the side port of the pump as described above.

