5.4 Study drug storage and accountability

The study drug (autologous MSC-NPs) is a biologic and each batch of drug is prepared according to each study subject's treatment schedule. Each study subject is given a unique alphanumeric ID that is used to label all cells derived from that patient. Each ID is recorded in a study subject ID assignment log that documents the patient's name and information. The log will be kept in a secure data base accessible only by un-blinded investigators.

Cryopreserved cells (MSCs) can be stored indefinitely with no expiration date. Any unused, cryopreserved cells will be donated for research purposes after the trial is completed, as detailed in the informed consent form. Expanded cells (MSC-NPs) are harvested just prior to the injection and injected within an hour after preparation. There is no storage period and no shipping. A sample of the final product MSCNP cells is preserved for quality testing purposes. These cells are lysed for RNA extraction. All commercial reagents will be used within manufacturers' expiration dates.

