8.2.2.2 Causality and severity assessment

One of the safety assessments neurologist (sub-Investigators [name] or [name]) of the trial will promptly review documented adverse events and abnormal test findings to determine 1) if the abnormal test finding should be classified as an adverse event; 2) if there is a reasonable possibility that the adverse event was caused by the study drug(s); and 3) if the adverse event meets the criteria for a *serious adverse event*.

If the final determination of causality is “unknown and of questionable relationship to the study drug(s)”, the adverse event will be classified as *associated with the use of the study drug(s)* for reporting purposes. If the final determination of causality is “unknown but not related to the study drug(s)”, this determination and the rationale for the determination will be documented in the respective subject’s case history.

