## 4.2 Analysis of the Secondary Study Objective

### Safety Analysis

All observed or volunteered adverse events (serious or non-serious) and abnormal test findings, regardless of study group or suspected causal relationship to the study drug(s) will be recorded in the subjects' case histories and submitted for yearly reporting to the DSMB and FDA. For safety analysis, the following will be tabulated:

- Incidence of Adverse Events
- Relationship pf Adverse Events to Investigational Product

**Study Name:** Autologous, Bone Marrow-Derived Mesenchymal Stem Cell-Derived Neural Progenitor Cells, Expanded Ex Vivo; Administered Intrathecally (Phase II Trial)

**Principal Investigator:** [name]

- Severity of Adverse Event
- Serious Adverse Events
- Adverse Events Leading to Treatment Discontinuation
- Death
- Adverse Events of Special Interest

Summary descriptive statistics will be reported for each adverse event. For continuous outcome, mean(sd)/median(IQR) for whole sample and each group will be reported along with p-values from two-sample two-sided t-test or Wilcoxon rank-sum test as appropriate. For binary outcomes, number (%) of events will be reported along with p-values from Chi-squared test or Fisher's exact test as appropriate. Linear or logistic regression will be applied to estimate the treatment effect on each safety outcome. Analyses will be performed at the end of each of the three years.

All analyses will be performed in SAS Version 9.4 (SAS Institute Inc., Cary, NC) or R version 4.0.3 (2020-10-10).

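### Causality and follow-up to resolution are tied to the cells alone, so an event clearly caused by marrow aspiration, antibiotic infusion or lumbar puncture has no causal class and need not be followed to its end

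*Protocol*

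**What the plan says.** Four places tie attribution or follow-up to one agent.

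- **Protocol 5.4** identifies that agent: "The study drug (autologous MSC-NPs) is a biologic". Section 5 describes the drug in the same way.
- **Protocol 8.2.2** requires the site to collect, for every event, enough information for "an assessment of the causal relationship between the adverse event and the study drug(s"). It then limits continued follow-up: "Adverse events or abnormal test findings felt to be associated with the study drug(s) will be followed until the event (or its sequelae") or finding resolves or becomes acceptably stable.
- **Protocol 8.2.2.2** has the safety neurologist decide "if there is a reasonable possibility that the adverse event was caused by the study drug(s"). An event judged "unknown and of questionable relationship to the study drug(s") is classed as associated with the drug for reporting purposes.
- **SAP 4.2** lists the table "Relationship pf Adverse Events to Investigational Product" and no other relationship table.

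Two further places do not match these. Protocol 8.3.2, on reports to the IRB, uses a wider term that takes in study treatments as well as the investigational drug. Protocol 9.4 begins the coded safety summary at the first lumbar puncture.

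The regimen contains more than cells. Section 5.1 states: "Prior to all lumbar punctures, a trained infusion nurse will infuse patients with 1 gram of vancomycin and 80 mg of tobramycin". At the six placebo visits "subjects will undergo standard lumbar punctures as described above but with no cell injections" (5.2.2). Section 6.2 adds a marrow aspiration about three months before treatment starts and a sampling puncture at month 27.

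**The concern.** The secondary objective is the safety and tolerability of repeated intrathecal injections. A patient cannot receive the cells without the marrow harvest, the antibiotic cover and the puncture, so their harms belong to the safety profile of the regimen.

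The protocol treats each of these as a hazard. It chooses a needle to reduce puncture headache, gives antibiotics against meningitis, excludes patients allergic to those antibiotics, and excludes blood disease because aspiration is invasive. Yet the causal assessment has no place for an event that the assessor believes came from one of them. The available answers are related to the drug, doubtful (which defaults to the drug) or not related.

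Two things are at stake. A participant harmed by a study procedure is not covered by the rule that events be followed to their end. And outcome and duration data would be more complete for events attributed to the cells than for events attributed to procedures.

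**Working it through.** **Exposure count.** Inputs per completing subject: 6 cell procedures and 6 placebo procedures (Protocol summary table), plus 1 sampling puncture at month 27 (Protocol 5.6 and 6.2).

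- Total punctures: 6 + 6 + 1 = 13. This reproduces the 13 CSF samples in the exploratory outcomes of SAP 4.1.
- Without cells: 6 + 1 = 7, and 7/13 = 53.8%.
- Treatment phase only: 6/12 = 50%. The majority therefore rests on the month-27 puncture.
- If all 50 subjects complete: 50 × 13 = 650 punctures, 50 × 7 = 350 without cells. With 40 completers: 520 and 280.
- Antibiotic infusions: 12 per subject, or 13 if the instruction in 5.1 covers month 27. For 50 subjects: 600 to 650.
- Marrow aspirations: at most one per subject, since 6.2 allows previously harvested marrow.

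The counts assume that every visit is completed and that no subject is dosed through a pump side port, which replaces the puncture (5.2.2).

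**Tracing events through the rules.** What matters is which events the wording leaves out.

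| Event | Can it be drug-related under 8.2.2.2? | Must it be followed to resolution under 8.2.2? | Is it in the 9.4 summary? |
|---|---|---|---|
| Harm from marrow aspiration, about month -3 | No, no cells yet given | No | No, if it occurs before the first puncture |
| Reaction during the month 0 antibiotic infusion | No, the infusion of about four hours comes first | No | Yes if the start is read by date; unclear if by time |
| Clear puncture complication after month 27 | Not on its face; the procedure delivers no cells | No | Yes |
| Puncture complication at a year-1 placebo visit | Possibly, since the assessor is blinded | Depends on the judgement | Yes |

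The first three rows do not depend on knowing the allocation. They are excluded by a stated rule.

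**Scheduled contact as a substitute.** Safety calls follow treatment visits only. Protocol 6.3 lists calls at 48 hours, 1 week and 1 month, which over 12 visits is 3 × 12 = 36, but gives a total of 24. That total equals 2 × 12 and matches the two calls in the schedule table, so the one-month call is not assured. After month 27 no call is planned, and the next visit is month 36, nine months later.

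**The case against.** The case on the other side is substantial.

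- **Events are not ignored.** All are recorded whatever the arm or cause, all are adjudicated by a safety neurologist, subjects have a 24-hour hotline, and serious events reach the DSMB within 24 to 48 hours. This stands. A reader might infer that procedural events need not be followed at all; the documents support only that they need not be followed to resolution. The requirement to pursue enough information on every event does not close the gap, because the outcome it mentions is explained as deciding whether the event is serious.
- **The arm tables show background harm.** SAP 4.2 also tabulates incidence, severity, serious events and discontinuations by group, without regard to attribution. In year 1 the placebo column carries punctures, CSF withdrawal, saline and antibiotics without cells. A reader might infer that procedural harms can appear nowhere except the relationship table. That is wrong: the difference between arms removes them, but the columns show them. What the columns cannot show is which component was responsible, or marrow harms before the first puncture.
- **Blinding and the default widen the rule in practice.** Follow-up turns on what is felt to be associated, only two investigators are unblinded (3.2), and neither is a safety neurologist. Many events at placebo visits may be felt drug-related and so followed. This stands. A reader might take the 350 cell-free punctures as a count of uncovered events; they are not. The default is limited to reporting and does not reach an event whose procedural cause is clear.
- **The term may be looser than 5.4 suggests.** The summary table counts placebo punctures among the 12 treatments, placebo supply sits under the study drug heading, and 8.3.2 is wider. This is a reason to reconcile the wording, since no section says how the wider judgement is made.
- **Attribution within one visit of about five hours is imprecise.** True, and it argues against splitting causes finely.

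**Conclusion.** The point holds in a limited form. Protocol 8.2.2 and 8.2.2.2 and SAP 4.2 leave an event clearly caused by marrow aspiration, antibiotic infusion or lumbar puncture without a causal class and outside the duty of follow-up to resolution. Marrow events before the first puncture also drop out of the safety summary. The gap is surest for the marrow aspiration, for an infusion reaction at month 0 and for the month-27 puncture; at placebo visits it depends on the blinded assessor's judgement.

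The size can be given only as exposure: 7 of 13 planned punctures per completing subject are without cells, a narrow majority that becomes an even split in the treatment phase. The documents give no event rates for the procedures, so the number of events affected cannot be estimated. The conclusion rests on reading study drug as 5.4 does. It does not bear on the efficacy analysis or on the comparison of event incidence between arms. It is worth correcting because it concerns participant safety and the change is small.

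**What to change.** - **Protocol 8.2.2:** extend follow-up until resolved or stable to all adverse events, or at least to those felt related to the study drug or to any study procedure.
- **Protocol 8.2.2.2:** add a separate judgement by the blinded safety neurologist of relationship to study procedures: puncture and injection, antibiotic infusion, marrow aspiration. A finer split is optional.
- **Protocol 9.4:** start the safety summary at the marrow aspiration and show pre-treatment events separately. Without this, a marrow category would stay largely empty.
- **SAP 4.2:** tabulate relationship to procedure beside relationship to product, by arm.
- **Protocol 8.3.2:** reconcile its wider wording with 8.2.2 and 8.2.2.2, so that one defined judgement serves both.

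The cost is wording in the protocol and SAP, a few fields on the adverse-event form and some further follow-up contacts. It needs no added patients or procedures. The remaining weakness is that attribution among components given at the same visit will be imprecise, so those tables should be read as descriptive.

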8.2.2.1 Abnormal test findings

An abnormal test finding will be classified as an *adverse event* if one or more of the following criteria are met:

- The test finding is accompanied by clinical symptoms
- The test finding necessitates additional diagnostic evaluation(s) or medical/surgical intervention; including significant additional concomitant drug treatment or other therapy
 - Note: simply repeating a test finding, in the absence of any of the other listed criteria, does not constitute an adverse event.
- The test finding leads to a change in study drug dosing or discontinuation of subject participation in the clinical research study
- The test finding is considered an adverse event by the Sponsor-Investigator of the IND application

8.2.2.2 Causality and severity assessment

One of the safety assessments neurologist (sub-Investigators [name] or [name]) of the trial will promptly review documented adverse events and abnormal test findings to determine 1) if the abnormal test finding should be classified as an adverse event; 2) if there is a reasonable possibility that the adverse event was caused by the study drug(s); and 3) if the adverse event meets the criteria for a *serious adverse event*.

If the final determination of causality is “unknown and of questionable relationship to the study drug(s)”, the adverse event will be classified as *associated with the use of the study drug(s)* for reporting purposes. If the final determination of causality is “unknown but not related to the study drug(s)”, this determination and the rationale for the determination will be documented in the respective subject’s case history.

8.3 Reporting of adverse reactions

8.3.1 Reporting of adverse reactions to the FDA

8.3.1.1 Written IND Safety Reports

The Sponsor-Investigator will submit a written IND Safety Report (i.e., completed FDA Form 3500 A) to the responsible new drug review division of the FDA for any observed or volunteered adverse event that is determined to be a *serious and unexpected, suspected adverse reaction*. Each IND Safety Report will be prominently labeled, “IND Safety Report”, and a copy will be provided to all participating investigators (if applicable) and sub-investigators.

Written IND Safety Reports will be submitted to the FDA as soon as possible and, in no event, later than 15 calendar days following the Sponsor-Investigator’s receipt of the respective adverse event information and determination that it meets the respective criteria for reporting.

For each written IND Safety Report, the Sponsor-Investigator will identify all previously submitted IND Safety Reports that addressed a similar suspected adverse reaction experience and will provide an analysis of the significance of newly reported, suspected adverse reaction in light of the previous, similar report(s) or any other relevant information.

Relevant follow-up information to an IND Safety Report will be submitted to the applicable review division of the FDA as soon as the information is available and will be identified as such (i.e., “Follow-up IND Safety Report”).

If the results of the Sponsor-Investigator’s follow-up investigation show that an adverse event that was initially determined to not require a written IND Safety Report does, in fact, meet the requirements for reporting; the Sponsor-Investigator will submit a written IND Safety Report as soon as possible, but in no event later than 15 calendar days, after the determination was made.

8.3.1.2 Telephoned IND Safety Reports – Fatal or life-threatening suspected adverse reactions

In addition to the subsequent submission of a written IND Safety Report (i.e., completed FDA Form 3500A), the Sponsor-Investigator will notify the responsible review division of the FDA by telephone or facsimile transmission of any *unexpected, fatal or life-threatening suspected adverse reaction*.

The telephone or facsimile transmission of applicable IND Safety Reports will be made as soon as possible but in no event later than 7 calendar days after the Sponsor-Investigator's receipt of the respective adverse event information and determination that it meets the respective criteria for reporting.

8.3.2 Reporting adverse events to the responsible IRB

In accordance with applicable policies of WIRB (Western Institutional Review Board), the Sponsor-Investigator will report, to the IRB, any observed or volunteered adverse event that is determined to be 1) *associated with the investigational drug or study treatment(s)*; 2) *serious*; and 3) *unexpected*. Adverse event reports will be submitted to the IRB in accordance with the respective IRB procedures.

Applicable adverse events will be reported to the IRB as soon as possible and, in no event, later than 10 calendar days following the sponsor-investigator's receipt of the respective information. Adverse events which are 1) *associated with the investigational drug or study treatment(s)*; 2) *fatal or life-threatening*; and 3) *unexpected* will be reported to the IRB within 24 hours of the Sponsor-Investigator's receipt of the respective information.

Follow-up information to a reported adverse event will be submitted to the IRB as soon as the relevant information is available. If the results of the Sponsor-Investigator's follow-up investigation show that an adverse event that was initially determined to not require reporting to the IRB does, in fact, meet the requirements for reporting; the Sponsor-Investigator will report the adverse event to the IRB as soon as possible, but in no event later than 10 calendar days, after the determination was made.

